Aim 1: Feasibility will be assessed through examination of participant recruitment, retention and engagement. Specifically, we will look at the number of participants who refuse to participate in the pilot at the time of recruitment and the reason they declined participation. Secondary impacts of interest include: medication adherence as measured by the four-item MA Questionnaire (MAQ) and change in systolic and diastolic blood pressure at 3 months.

Aim 2: To test the acceptability of a 3-month SMS-based intervention in adults with uncontrolled hypertension. One cohort of 24 participants will be recruited for the SMS intervention. Acceptability will be assessed using the systems usability scale (a validated questionnaire that measures usability reliably in small samples)¹⁸ and eliciting free comments after the survey.

At the end of this pilot project, we will have preliminary data essential for a future formal efficacy trial, to be proposed in a subsequent application to the AHRQ.

Our **first hypothesis** is that over 50% of contacted patients will respond to SMS messages and over 50% will check HBPM. This estimate is based on previous study by Bobrow and

colleagues in a similar patient population.³ Our **second hypothesis** will be that > 75% will be satisfied with the service (OK or above on the usability survey).⁹

Methods and Measures

Design

A randomized control trial of 24 non-adherent participants will be monitored and followed for 3 months; An ambulatory BP arm device will be provided to all participants with printed instructions in English or Spanish (from the American Heart Association) on how to measure BP at home (HBPM). Patients will be instructed on checking their BP at least twice a week.^{14,19} Text messages will be generated by Twilio platform, keeping a record of participants contacted, sent and received texts. Participants in the control arm will receive standard of care education for controlling high blood pressure in clinic by their healthcare providers. They will be followed to monitor any changes in their BP throughout the duration of the study.

Study team members will identify patients with uncontrolled hypertension during clinic visits. Study team members will approach patients 18 years or older who have uncontrolled HTN (SBP>130 or DBP >80) and have 2 or more BP medication(s) on their medication list.

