recommendations by HTN guidelines, which designate a hypertensive urgency to be 180/110 mm Hg or higher and hypotension 90/60 or lower.²

Patients who no show to the follow up visits will be telephoned to assess adherence barriers. The study team member will create a telephone encounter in the electronic health record to document their discussion and route it to the patient's PCP. Patients who refuse participation in the study will be asked for the reason and their responses will be recorded to determine any barriers to participation. Study team members will attempt to contact patients who miss follow up visits every week up to 3 times, if after the 3rd time the patient is still not able to be reached, the patient will be lost to follow up.

Setting

The study team will recruit patients who fall within the eligibility criteria from Wake Forest Baptist Medical Center.

Subjects selection criteria

Eligibility and recruitment

Inclusion criteria

Patients 18 years and older who have SBP>130 or DBP >80 during an office visit encounter in the past 6 months and have BP medication(s) on their medication list.

- Own a phone with SMS capability
- Non-adherent-MAQ score of 1 to 4
- Vulnerable population (Black, Hispanic or education level < or equal high school (as an indicator of low SES)

Exclusion Criteria

- End-stage renal disease (on hemodialysis or peritoneal dialysis)
- Kidney transplant recipients
- Unable to afford BP medications or lack transportation to clinic visits
- Hospice or nursing home care
- Dementia or cognitive impairment on the problem list

Sample Size

24 patients –We will randomize 12 patients into 2 groups

Interventions and Interactions

Pilot randomized controlled study.

Participants in the SMS intervention arm will receive usual care and SMS texting and phone calls. Study team members will send secure SMS messages to participants weekly for four weeks and then every other week until their next appointment.

The secure messaging system will be as follows

Introductory message:

Welcome to managing your blood pressure with the Nephrology/ Internal medicine clinics at Wake Forest. Try to take your BP meds at the same time every day to keep your BP under control! Make it part of your daily routine:

First week

Adherence checkpoint:

1. *Good morning! Did you take your blood pressure medications today?*

“No” Response:

1. *Let's try to stay on top of taking them daily! You can do this!*

Additional prompts:

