1. Screening: we will track the number of patients screened per month, the number enrolled per month, the proportion that are eligible who enroll.
2. Recruitment: number of participants who refuse to participate in the pilot at the time of recruitment and the reason why. Proportion of vulnerable patients screened but excluded because they did not own a phone with SMS capability.
3. Retention: the proportion of participants who continue to use the myHealth tool per month through three months will be tracked for the intervention.
4. Engagement: 12- SMS rate response of at least one home BP measurement. We will use 44% as our cut off based on an SMS study by Peters and colleagues²⁵.

Finally, we will monitor time needed for assessments and gather feedback on the participant burden.

B-Acceptability

Participants will complete the SUS in person on an I-Pad or over the phone. They will also be offered the opportunity to comment in their questionnaires about their experiences of taking part in the pilot. The SUS yields a single score on a scale of 0–100. A SUS score above a 68 would be considered above average. We will consider acceptable when >70 % of participants score the SUS above 68.²⁶

Secondary measures of interest

Medication adherence (MA) will be measured by administrating the four-item MAQ by the study coordinator during enrollment and at 3 months follow up visit. The MAQ was selected because it has been well-validated to identify adherence in HTN and scores have been shown to correlate well with a range of objective adherence measures.^{11,12}

SBP and DBP change at 3 months. BP will be measured during initial and follow up office visits by nurses or clinicians while patient is seated with automated arm devices according to standard office procedures. We will extract from the electronic medical record, SBP and DBP at enrollment and at 12 weeks follow up. The average change will be calculated and reported in mmHg.

No-show rate at 3 months' follow-up (f/u) clinic visits. If participants fail to come to their f/u visits within 7 days of their scheduled follow-up appointment, they will be considered as "no-shows". Our current clinic no-show rate is 30%, therefore if the study participants no-show rate is less than 30% we will consider our tool a feasible intervention.

Analytical Plan

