Results will be analyzed initially using descriptive statistics. Comparison between groups will be done using chi square tests for proportions, and t-tests for continuous variables. Regression analysis will be performed to identify independent outcome predictors. RedCap will be utilized to collect all patient data. Participant's demographics (including education level), co-morbidities, number of medications, number of blood pressure medications and BP numbers will be extracted from Wake One when available. Level of education will be confirmed verbally with each participant during consent process. Only one participant identifier will appear in the data collection forms.

The full analysis set will include participants who have responded to at least one SMS message post-randomization. Descriptive statistics will be computed for each treatment group; medians and percentiles will be reported for skewed continuous variables. For primary and secondary outcomes, descriptive statistics and 95% confidence intervals will be used to summarize the differences between groups. The secondary outcome of BP and other continuous variables will be assessed with a repeated-measures analysis using a mixed linear model approach. The Wilcoxon rank sum test will be used to compare MA between groups. Hypothesis tests will be 2-sided using the 0.05 significance level. Bonferroni-type adjustments for multiple testing will be implemented to control type I errors. Statistical analysis will be performed using SAS software (SAS Institute, Cary, NC).

Treatment assignment will be determined using blocked randomization

The primary analysis will consist of all subjects who responded with at least one BP measurement

Human Subjects Protection

Subject Recruitment Methods

Subjects will be identified when they come to an office visit and their blood pressure is not well controlled. The PI clinician (internal medicine preceptors or residents) will verbally alert the study coordinator on site of possible participants based on BP >140/90. The study team member will meet the patient in a private room in 7th Janeway, determine eligibility, and signed informed consent will be obtained from each subject. Once enrolled, the subjects will be contacted by phone via SMS and phone call. To ensure equal access to participation among women and minorities we will translate all materials and questions to Spanish. The privacy of

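### No adjustment for enrolment BP is specified for the BP comparison; specifying it would give a modestly tighter estimate, less exposed to chance imbalance, for one degree of freedom

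*Combined protocol and SAP*

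**What the plan says.** Under Secondary measures of interest, the BP outcome uses "SBP and DBP at enrollment and at 12 weeks follow up", taken from the electronic record, and "The average change will be calculated and reported in mmHg". The Analytical Plan opens with a general sentence that assigns "t-tests for continuous variables" to group comparisons. It later gives BP its own method: "The secondary outcome of BP and other continuous variables will be assessed with a repeated-measures analysis using a mixed linear model approach". Fixed effects, covariance structure, treatment contrast and the role of the enrolment reading are not stated.

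The only regression sentence is a general search for outcome predictors; it names no covariate and is not tied to the arm comparison. Randomisation is blocked, with no stratification by BP mentioned. The same section promises 95% confidence intervals for differences between groups on primary and secondary outcomes.

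**The concern.** Enrolment BP is usually the best available predictor of week-12 BP, and the plan already extracts it. Using it as a covariate, or constraining the arms to a common baseline mean, removes the part of the arm difference that chance imbalance at enrolment explains. Neither device is specified.

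The label of a repeated-measures mixed model does not settle this. Different models under that label estimate different quantities, and one common specification returns the change-score difference. A change score over-corrects when the correlation between visits is below 1: the arm that happens to start higher appears to fall more. A comparison of week-12 values alone errs the other way. At 12 per arm or fewer, such imbalance is a practical matter. What is at stake is the precision and stability of the BP difference that the pilot will report.

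**Working it through.** **Inputs from the document.** Sample Size gives a total of 24 and says "We will randomize 12 patients into 2 groups"; Design says "A randomized control trial of 24 non-adherent participants will be monitored and followed for 3 months". I read this as 12 per arm. On testing: "Hypothesis tests will be 2-sided using the 0.05 significance level". Also "Bonferroni-type adjustments for multiple testing will be implemented to control type I errors", but the number of tests is not given, so the intervals below are unadjusted 95% intervals. BP time points are enrolment and 12 weeks.

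**Assumptions.** The document gives no BP SD, between-visit correlation (rho), target difference or power, so there is no stated figure to reproduce. I take SD 15 mmHg at both visits and rho from 0.2 to 0.7.

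**What the mixed model estimates.** With both visits as outcomes, a free mean for each arm at each visit and complete data, the fitted means are the observed means. The arm-by-visit contrast is then the difference in mean change. One simulated data set of 12 per arm bears this out:

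- free baseline means: 8.16 (SE 6.12), identical to the change-score difference of 8.16
- common baseline mean: 7.50 (SE 5.53)
- enrolment BP as covariate: 7.44 (SE 5.49)
- arm main effect across both visits: 2.24, the average of the enrolment and follow-up differences

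**Variance of the arm difference, n = 12 per arm.** Let V = 2 × SD² / n = 2 × 225 / 12 = 37.5.

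- Follow-up only: V, with 22 df.
- Change score: V × 2(1 − rho), with 22 df.
- Adjusted: V × (1 − rho²) × (1 + 1/(2n − 4)) = V × (1 − rho²) × 1.05, with 21 df. The factor 1.05 is the cost of estimating the slope.

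At rho 0.5:

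- Change score: 37.5 × 1 = 37.5; SE 6.12; half-width 2.074 × 6.12 = 12.7 mmHg.
- Adjusted: 37.5 × 0.75 × 1.05 = 29.5; SE 5.43; half-width 2.080 × 5.43 = 11.3 mmHg.

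| rho | Half-width, follow-up only | Half-width, change | Half-width, adjusted | Variance, adjusted / change | Variance, adjusted / follow-up only |
|---|---|---|---|---|---|
| 0.2 | 12.7 | 16.1 | 12.8 | 0.63 | 1.01 |
| 0.3 | 12.7 | 15.0 | 12.4 | 0.68 | 0.96 |
| 0.5 | 12.7 | 12.7 | 11.3 | 0.79 | 0.79 |
| 0.7 | 12.7 | 9.8 | 9.3 | 0.89 | 0.54 |

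Simulation (40,000 trials per rho) agreed: at rho 0.5 the empirical SEs were 6.13 (follow-up only), 6.13 (change) and 5.43 (adjusted).

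**Chance imbalance.** The SE of the enrolment difference is 15 × √(2/12) = 6.12 mmHg. The probability of a gap of 5 mmHg or more is 2 × (1 − Φ(5/6.12)) = 41%; it is 31% at SD 12 and 54% at SD 20. A gap of one SE shifts the follow-up comparison by rho × 6.12 and the change comparison by (rho − 1) × 6.12. At rho 0.5 these are +3.1 and −3.1 mmHg; at 0.3, +1.8 and −4.3; at 0.7, +4.3 and −1.8. Adjustment removes the expected shift.

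**Fewer participants.** The outcome section cites a 30% clinic no-show rate; 12 × 0.7 is about 8 per arm. The factor becomes 1 + 1/12 = 1.083, and at rho 0.5 the half-width goes from 16.1 (change) to 14.6 mmHg (adjusted).

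**The case against.** **Silence is not exclusion.** A reader might infer that the plan rules out baseline adjustment. It does not: the mixed-model sentence is open, and a model with a common baseline mean would fit it. The text supports only that no adjustment is specified. This stands.

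**One method or several.** A reader might infer that the plan sets competing tests for BP. The t-test sentence is general, and the later BP sentence can reasonably be read as governing; average change may be only a descriptive summary. This stands too, although the document does not say that the general sentence excludes BP.

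**The gain may be smaller.** Participants are selected on raised BP, which narrows the enrolment spread. As an extreme illustration, take an unselected SD of 15 mmHg and truncation of the enrolment reading at its mean, so that the enrolment SD is 15 × √(1 − 2/π) = 9.0. The chance of a 5 mmHg gap falls from 41% to 18%. The variance gain over change scores falls to about 12%, 6% and 1% at rho 0.3, 0.5 and 0.7, where rho is the correlation before selection, and the half-width at 0.5 goes only from 11.6 to 11.3 mmHg. Actual selection is milder, because either SBP or DBP can qualify and the qualifying reading may be up to six months old. The direction of the objection holds.

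**Availability and importance.** The Analytical Plan extracts BP when available, so a complete set of enrolment values is not guaranteed. Feasibility and acceptability are the aims, BP is secondary, and no decision rule depends on it. An interval of ±11 or ±13 mmHg says little about efficacy either way. All of this limits the importance; none of it removes the gain.

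**Conclusion.** The point holds as a cheap improvement, of minor-to-moderate weight. The plan reports change and names a mixed model whose usual free-baseline form gives the change-score estimate. Specifying adjustment would lower the variance against that estimate by about 32%, 21% and 11% at rho 0.3, 0.5 and 0.7. These figures assume SD 15 mmHg at both visits and a full 12 per arm, and they shrink if selection narrows the enrolment spread. Against a follow-up-only comparison the gain is about 4% at rho 0.3, absent near 0.2, and a loss of up to 5% at rho 0.

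Two stronger readings are not supported. A reader might infer that the planned BP estimates are biased. Under randomisation each is unbiased on average if all randomised participants are analysed; the exposure is to imbalance in the sample actually drawn. A reader might also infer that the later efficacy trial will be sized on this BP estimate. Specific Aims promises preliminary data for that trial but does not say so.

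Twelve per arm is a ceiling. The Analytical Plan restricts its analysis sets to people who answered a text or returned a BP reading, and some week-12 readings will be missing. These are separate problems that baseline adjustment does not repair.

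**What to change.** In the Analytical Plan, name one main BP analysis, for SBP and DBP separately. Either of these would do:

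- a linear model of week-12 BP on arm, with the enrolment value of the same measure as covariate; or
- a constrained longitudinal mixed model with enrolment and week 12 as outcomes, a common enrolment mean and an arm effect at week 12 only.

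State that the treatment effect is the week-12 arm difference and report it in mmHg with its 95% confidence interval. Keep average change by arm as a descriptive summary if wanted, and state that the general t-test sentence does not apply to BP.

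The cost is a few lines of text and one degree of freedom, with no new data. At 12 per arm the small-sample penalty is the 5% factor shown above, which leaves a net loss only against a follow-up-only comparison at rho of about 0.2 or below.
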